We enhanced the motivation phase of the conceptual model with additional components drawn from risk perception and communication research. Comprehension of information was added because perceptions and comprehension are slightly different constructs that each have an important role in influencing health behavior and decisions.^[11] Worry, affective reaction to the information, affective attitudes to exercise, and anticipated regret were added because a growing body of research demonstrates that affect and emotion are integral to the formation of risk perceptions, in increasing motivation to change behavior, and in changing behavior itself.^[12-17] Demographics, numeracy, health literacy, and graph literacy were added because they are associated with the ability to understand and use health risk information.^[18-20]

According to HAPA, progression to the **action phase** is dependent upon factors not included in the motivation phase. These new factors include developing action plans for engaging in the behavior, coping plans for overcoming barriers to action, maintenance self-efficacy (i.e., confidence in the ability to overcome barriers to acting), and recovery self-efficacy (i.e., confidence in the ability to recover from a relapse).

Objectives

RISK CALCULATOR

To compare the effectiveness of communicating personalized risk estimates via text, table, or risk ladder.

Primary outcomes hypotheses and exploratory research questions

H1: Comprehension of risk information and intentions to increase physical activity will be higher among individuals who see multiple disease risks presented as a risk ladder than as text.

RQ1: Prior research has shown that tables can be effective in communicating risk information.^[21] Compared to the table, will the risk ladder elicit higher comprehension and intentions?

Secondary outcomes hypotheses and exploratory research questions

H2: Any significant effect of the risk ladder on intentions will be mediated by comprehension, risk perceptions, response efficacy, worry, affective reactions to information, affective attitudes to exercise, and anticipated regret.

H3: Engagement in physical activity will increase from baseline to 90 day follow-up to a greater extent for individuals who see the risk ladder than those who see text only.

H4: Intentions will mediate any significant effect of the risk ladder on physical activity.

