All hypotheses and research questions will be examined using separate analyses for each outcome variable. Assumptions of each type of test will be checked (e.g., assumptions of normality and homogeneity of variance for ANOVAs). If there are violations, non-parametric tests will be used instead. Sex will be a covariate because there are no valid prediction models for male breast cancer, so men will not be shown a breast cancer risk estimate. The inclusion of other personal characteristics as covariates will be determined by the results of the preliminary analyses. Tests of moderation will be conducted by creating interaction terms between the risk presentation condition or mental imagery condition variables, as appropriate, and the variable assessing the moderator of interest. All statistical tests will be based on list-wise deletion except structural equation models, which can accommodate missing data.

Mediation analyses will be conducted using structural equation modeling (SEM). Full Information Maximum Likelihood estimation (FIML)^[44] will be used to allow the inclusion of missing data. Standardized estimates will be calculated and bias-corrected bootstrapping will be used to obtain the 95% confidence intervals.^[45-48] Criteria assessing model fit will also be examined (e.g., Standardized Root Mean Square Residual $\leq .08$, comparative fit index $\geq .95$, root mean square error of approximation $\leq .06$).^[49, 50] Mediation analyses will examine each construct as an individual mediator first, and then as a multiple mediator model.

Table 2 below describes the analyses that will be conducted for each hypothesis or research question.

Table 2. Overview of Statistical Analyses

	Priority	Statistical test(s)	Outcomes	Predictors/Mediators/Moderators
Risk Calculator				
H1; RQ1	Primary	3 arm ANOVA, 2 planned contrasts (risk ladder vs. text; risk ladder vs. table)	Comprehension, intentions	Predictor: Risk presentation condition
H2	Secondary	SEM	Intentions	Predictor: Risk presentation condition (risk ladder vs. text) Mediators: comprehension, risk perceptions, response efficacy, worry, affective reactions to information, affective attitudes to exercise, anticipated regret
H3	Secondary	3 arm ANOVA, planned contrast (risk ladder vs. text)	Change in physical activity (mins/week at 90 days – mins/week at baseline)	Predictor: Risk presentation condition

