H4	Secondary	SEM	Change in physical activity (mins/week at 90 days – mins/week at baseline)	Predictor: Risk presentation condition (risk ladder vs. text) Mediator: Intentions
RQ2	Secondary	3 arm ANOVA, planned contrast (risk ladder vs.	Risk perceptions, response efficacy, worry, affective reactions to information, affective attitudes	Predictor: Risk presentation condition

table) to exercise, anticipated regret

RQ3 Secondary 3 arm ANOVA Comprehension, intentions Predictor: Risk presentation condition
Moderators: Education, race/ethnicity, numeracy, health and graph literacy

Mental Imagery

H5	Primary	T-test	Change in physical activity (mins/week at 90 days – mins/week at baseline)	Predictor: Mental imagery condition
RQ5	Primary	ANOVA	Change in physical activity (mins/week at 90 days – mins/week at baseline)	Predictor: Mental imagery condition Moderators: Education, race/ethnicity, numeracy, health and graph literacy
H6	Secondary	Regression (physical activity mental imagery condition only)	Change in physical activity (mins/week at 90 days – mins/week at baseline)	Predictors: Week 4 action planning, coping planning, action self-efficacy, maintenance self-efficacy, recovery self-efficacy, affective attitudes to exercise, perceived vividness
RQ6	Secondary	Regression (physical activity mental imagery condition only)	Weekly change in minutes of physical activity, assessed by 4 difference scores: Week1-Baseline; Week2-Week1; Week3-Week2; and Week4-Week3	Predictors: For each weekly behavioral assessment, use the previous week's measures of the following constructs: action planning, coping planning, action self-efficacy, maintenance self-efficacy, recovery self-efficacy, affective attitudes to exercise, perceived vividness.

Sample Size Calculations

We will enroll 500 participants at baseline. This will enable us to test the primary hypothesis for each of the components of the study. This calculation was based on the information below.

RISK CALCULATOR

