Sample size was calculated to be able to detect an effect of risk presentation strategy on the primary outcome variables comprehension and intentions (Risk Calculator Hypothesis 1 and RQ1). Based on a 2-sided test of means for 3 groups (ANOVA) at 80% power, $\alpha=.05$, $df=2$, and Cohen's f effect size of 0.15 (approximately equivalent to Cohen's d of 0.3),^[51, 52] we anticipate needing 432 participants. The effect size estimate was based on a study of personalized breast cancer risk and risk reduction communication that found an effect on intentions to increase physical activity of approximately $f=0.25$ and an effect on response efficacy of approximately $f=0.20$.^[4] However, most of those participants were white, highly educated, had high health literacy, and recruited from a breast health center. Thus, we can expect the findings in our more diverse sample to be somewhat lower. We chose $f=.15$ as a reasonable compromise because it represents slightly more than a minimal effect,^[53] but is also logistically feasible. To account for the possibility of 10% missing data in Baseline Survey 1, which assesses the constructs for the Risk Calculator Hypothesis 1, we would need to enroll 480 participants to obtain 432 completed surveys.

MENTAL IMAGERY

[name] prior self-regulatory intervention accounted for approximately 20% of the unique variance in physical activity at 4-week follow-up.^[5] This is approximately equivalent to a Cohen's d effect size of 1.0, which is considered a large effect.^[53] Because our follow-up is 90 days, we can expect that our effect size will be somewhat lower. Other self-regulation interventions yielded smaller effects over varying timeframes (e.g., $d=0.28-0.78$).^[7] Thus, powering the study to detect an effect of $d=0.30$ of the intervention on behavior (Mental

Imagery Hypothesis 5) would be conservative and reasonable. Based on a 2-sided test of means for 2 groups (t-test) at 80% power, $\alpha=.05$, and Cohen's d effect size of 0.30,^[51, 52] we anticipate needing 352 participants at 90-day follow-up. To account for the possibility of 30% attrition rate due to our underserved sample (unpublished data), we expect needing to enroll 500 participants at baseline to achieve this goal.

Study Procedure Calendar

	Year 1				Year 2				Year 3				Year 4			
	1	2	3	4	1	2	3	4	1	2	3	4	1	2	3	4
Startup (hiring, IRB amendments)	X	X	X	X					X							
Biweekly research team meetings	X	X	X	X	X	X	X	X	X	X	X	X	X	X	X	X

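### The risk calculator's 80% power belongs to the three-arm omnibus test at f = 0.15; the contrasts that answer H1 and RQ1 have no stated power, and the d = 0.3 gloss is a two-group conversion

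*Combined protocol and SAP*

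**What the plan says.** Under Statistical Considerations, Sample Size Calculations, the plan says of the 500 participants: "This will enable us to test the primary hypothesis for each of the components of the study". The Risk Calculator paragraph ties its calculation to Hypothesis 1 and RQ1, on comprehension and intentions. It describes the calculation thus: "Based on a 2-sided test of means for 3 groups (ANOVA) at 80% power", with alpha .05, df = 2 and "Cohen's f effect size of 0.15 (approximately equivalent to Cohen's d of 0.3". That gives 432 participants, and after a 10% allowance for missing data, "we would need to enroll 480 participants to obtain 432 completed surveys".

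The Mental Imagery paragraph sizes H5 as a two-group t-test at d = 0.30: "we anticipate needing 352 participants at 90-day follow-up".

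In Objectives, H1 is pairwise and directional. It begins "Comprehension of risk information and intentions to increase physical activity will be higher among individuals" and compares those who see the ladder with those who see text. RQ1 asks whether the ladder does better than the table. For both, Table 2 lists a three-arm ANOVA with "2 planned contrasts (risk ladder vs. text; risk ladder vs. table". No section gives a power or sample size for either contrast.

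**The concern.** The powered test and the test that answers the question differ. The omnibus F test asks whether the three means differ in any way. A significant result could come from the table arm alone and would not show that the ladder beats text. H1 and RQ1 need the contrasts.

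The d = 0.3 gloss hides this gap. It invites the reader to take the study as having 80% power for a ladder–text difference of about 0.3 standard deviations. If H1 came out null and were described that way, the statement would claim more sensitivity than the contrast had.

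**Working it through.** **Inputs.** From the plan: three arms of equal size (equal allocation over six cells), alpha .05 two-sided, f = 0.15, 432 completers (144 per arm), 10% missing, 500 enrolled. Derived here, not stated in the plan: 500 × 0.9 / 3 = 150 per arm. All power figures are per outcome, unadjusted for multiplicity and before covariates.

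**1. The plan's own figure.** Omnibus F, non-centrality λ = f²N, df = (2, N − 3). At N = 432, λ = 0.0225 × 432 = 9.72 and power is 0.8008; at N = 431 it is 0.7998. So 432 is exactly the smallest N for 80%, and 432 / 0.9 = 480. Both stated figures reproduce. At N = 450 the power is 0.818.

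**2. Where d = 0.3 comes from.** For two equal groups f = d/2, so f = 0.15 gives d = 0.30. For three equal arms, f² = (1/3) Σ(μᵢ − μ̄)²/σ², and the conversion depends on the third arm:

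- Third arm tied with one end: f = d√2/3, so d = 3 × 0.15/√2 = 0.318.
- Third arm midway: f = d/√6, so d = 0.15 × √6 = 0.367.

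Conversely, a largest difference of 0.30 means f = 0.141 (tied) or 0.122 (midway). Omnibus power at N = 432 is then 0.749 or 0.616.

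As a cross-check, the same F calculation with two groups and f = 0.15 gives N = 352, the plan's H5 figure for d = 0.30.

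**3. Power of a planned contrast.** Non-central t, non-centrality d√(n/2), df = 3n − 3. √(144/2) = 8.485 and √(150/2) = 8.660.

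| Difference between the two arms | 144 per arm | 150 per arm |
|---|---|---|
| d = 0.30 | 2.546 → 71.9% | 2.598 → 73.7% |
| d = 0.318 (f = 0.15, third arm tied) | 2.700 → 76.9% | 2.756 → 78.5% |
| d = 0.367 (f = 0.15, third arm midway) | 3.118 → 87.5% | 3.182 → 88.8% |

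The difference detectable with 80% power is d = 0.331 (144 per arm) or 0.324 (150 per arm).

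**4. When the contrast's two arms are not the extremes.** The plan states no pattern of means. For illustration only, suppose f = 0.15 and the third arm lies outside the pair by a quarter or a half of their gap. The pair's difference is then d = 0.278 or 0.241, and power with 150 per arm is 67.0% or 54.7%. Ladder–text and ladder–table can both be the extreme pair only if text and table tie. If table is midway between text and ladder, the ladder–table difference is only 0.367/2 = 0.184.

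**5. Covariates.** Sex is a fixed covariate and others may enter, but the plan gives no R². Using d/√(1 − R²) with assumed R² of 0.05, 0.10 and 0.15, the 73.7% at d = 0.30 (150 per arm) becomes 75.8%, 78.0% and 80.3%.

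**The case against.** The best defence is that nothing in the sample-size arithmetic is wrong. The only effect size used is f. The d = 0.3 is a bracketed remark, hedged and given to one decimal; it enters no calculation, and 0.318 rounds to it. At the actual design input, a contrast between the extreme arms has close to or above 80% power. With 150 per arm, ladder versus text reaches 80% once table lies about 4% of the way in from either end. Covariate adjustment would help further. All of this stands, and it is why the point concerns labelling and stated power.

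It does not remove the point. The same sentence attaches 80% power to d of about 0.3, the paragraph names H1 and RQ1 as its targets, and the tests that answer them are given no power.

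A reader might infer more than the documents support:

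- *That the study is too small or 432 is wrong.* It is not; 432 is right for the test and effect size specified.
- *That at d = 0.3 no test in the H1 row of Table 2 reaches 80%.* For the omnibus test at N = 432 this holds only if 0.30 is the largest of the three pairwise differences.
- *That the plan itself shows its d came from a two-group formula.* The plan gives 352 for a t-test at d = 0.30 and never mentions a two-group f; the match is a calculation made here.
- *That table is expected to fall outside the ladder–text range.* Objectives says only "Prior research has shown that tables can be effective in communicating risk information", which leaves this open but does not predict it.

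**Conclusion.** The point holds as a minor fault of labelling and reporting. The stated 80% is omnibus power at f = 0.15. At the plan's own 144 per arm, a contrast between the extreme arms ranges from about 3 points below that figure to about 7 above it. At the quoted d = 0.3 the contrast is about 8 points below, or about 6 with 150 per arm. How low contrast power could go at f = 0.15 cannot be settled from the documents, because no pattern of means is given.

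These results assume equal arms, a common variance, two-sided .05 for each outcome and no covariate adjustment. The figures for 150 per arm also assume that exactly 10% of Baseline Survey 1 data are missing, spread evenly over the arms.

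**What to change.** In the Risk Calculator paragraph of Sample Size Calculations, delete the bracketed equivalence to d = 0.3. Keep the derivation of 432 and 480, and add:

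> With 450 completed Baseline Survey 1 (150 per arm), the omnibus F test has 82% power for f = 0.15. Each planned contrast (ladder vs text for H1; ladder vs table for RQ1), two-sided .05, per outcome and before covariate adjustment, has about 79–89% power at f = 0.15 if its two arms are the extremes and less otherwise; it has 80% power for d = 0.32 and 74% for d = 0.30.

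The cost is one reworded paragraph and a slightly less favourable stated power for H1 and RQ1 at d = 0.30. Enrolment, tests and data collection do not change.

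### The H5 sample size allows for attrition but states no allowance for list-wise deletion among returned 90-day surveys; an adjusted analysis that keeps partial cases would protect those outcomes

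*Combined protocol and SAP*

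**What the plan says.** In the Combined protocol and SAP, Sample Size Calculations, Mental Imagery, the H5 calculation is "Based on a 2-sided test of means for 2 groups (t-test) at 80% power", with alpha .05 and Cohen's d of 0.30. From this, "we anticipate needing 352 participants at 90-day follow-up". Allowing for 30% attrition, "we expect needing to enroll 500 participants at baseline to achieve this goal".

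The Risk Calculator calculation just above it uses a different kind of allowance: "To account for the possibility of 10% missing data in Baseline Survey 1", it raises 432 to 480. That allowance is tied to Baseline Survey 1 and to H1.

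Statistical Considerations, Main Analyses, sets the missing-data rule: "All statistical tests will be based on list-wise deletion except structural equation models, which can accommodate missing data". The same section makes sex a covariate and leaves other covariates to the preliminary analyses. Under Preliminary Analyses, health status, numeracy, health literacy and graph literacy are among the characteristics screened. Any that differ between conditions or are associated with an outcome are carried forward as potential covariates. Table 1 places all four in Baseline Survey 1.

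Table 2 gives H5 as a t-test on 90-day minus baseline minutes per week. RQ5, also labelled primary, adds numeracy, health literacy and graph literacy as moderators of the same outcome.

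**The concern.** Attrition and list-wise deletion are different losses. Attrition removes people who do not return the 90-day survey. List-wise deletion removes people who did return it but lack some value that the model uses. The H5 calculation names only the first, and 500 leaves no margin for the second.

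There are two routes to that second loss. One is a returned survey with unusable activity items: the form is mailed and completed on paper, and participants may decline any question (Data and Safety Monitoring Plan, Voluntary participation). The other is a complete activity outcome discarded because a covariate from Baseline Survey 1 is blank. The second route is avoidable, because the outcome is in hand and only the analysis rule throws it away. At stake are a few points of power for the primary imagery hypothesis and the needless loss of data from a sample the investigators expect to be hard to retain.

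**Working it through.** **Inputs from the plan.** Two-sided t-test, alpha .05, 80% power, d=0.30, 30% attrition and 500 enrolled (Sample Size Calculations, Mental Imagery). Equal allocation to six cells, hence 1:1 by imagery condition (Research Plan, Design).

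**Reproducing 352.** With n per arm, the noncentrality is d x sqrt(n/2). Solving the noncentral t for 80% power gives n = 175.38, rounded up to 176 per arm, or 352 in total. This matches the plan.

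**Reproducing 500.** 352 / 0.70 = 502.9, so exact inflation gives 503. In the other direction, 500 x 0.70 = 350. Power is 80.1% at 352 and 79.9% at 350. The difference is rounding.

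**Adding a loss among returned surveys.** Let m be the fraction of returned surveys removed by list-wise deletion. The documents give no value for H5, so m is an assumption. N = 350 x (1 - m).

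| m (assumed) | N analysed | Power at d=0.30 |
|---|---|---|
| 0% | 350 | 79.9% |
| 2% | 343 | 79.1% |
| 5% | about 332 | 77.8% |
| 10% | 315 | 75.6% |

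At N = 315 the effect detectable with 80% power is d of about 0.317.

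**What baseline adjustment returns.** Let s be a common SD at baseline and 90 days, and r the correlation between them.

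- Variance of the change score: 2s²(1 - r).
- Residual variance after adjusting for baseline: s²(1 - r²).
- Ratio: (1 - r²) / [2(1 - r)] = (1 + r)/2.

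At an assumed r = 0.5 the ratio is 0.75, so the adjusted analysis needs 352 x 0.75 = 264 for the power that the change score gives with 352. Even a 10% loss is fully offset if (1 + r)/2 is at most 315/352 = 0.895, that is, for r up to about 0.79.

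**A limit on that gain.** Eligibility requires less than 150 minutes per week at baseline, so the baseline SD may be smaller than the 90-day SD. Let k be baseline SD divided by 90-day SD. The ratio becomes (1 - r²) / (1 + k² - 2rk). This never exceeds 1, because the denominator equals (1 - r²) + (k - r)², but it reaches 1 when k = r. For example, r = 0.5 and k = 0.5 give 0.75/0.75 = 1, which is no gain. Apart from the small cost of estimating the slope, adjustment does no worse than the change score. How much better it does depends on r and k, which the documents do not give.

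**The case against.** A reader might infer that 500 fails to deliver the stated power, or that the plan's own 10% brings H5 down to 315 participants. The documents support neither reading. The gap between 350 and 352 is rounding. The 10% belongs to Baseline Survey 1 and H1, whereas the H5 outcome is built from activity items in the eligibility screener and the 90-day survey. Attrition is not defined, so the 30% could cover everyone without usable 90-day data, and the two losses could overlap. The 10% may itself describe whole surveys not completed rather than blank items, since it is used to reach a number of completed surveys.

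Several sources of deletion are also unlikely. Baseline activity decides eligibility, and sex decides whether a breast cancer estimate is shown, so both should be known for enrolled participants. Table 2 lists imagery condition as the only H5 predictor, and further covariates enter only if the preliminary analyses select them. Numeracy and graph literacy are scored as number correct, so a blank might count as wrong rather than missing. Finally, d=0.30 lies near the bottom of the range of 0.28 to 0.78 that the plan cites, and the move to 0.317 is small.

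All of this stands, and it keeps the point minor. It does not remove the gap. The H5 calculation does not say whether item-level loss is inside the 30%. List-wise deletion applies to H5 without a stated reason. Health status and health literacy have no scoring rule that would absorb a blank, and both can enter as covariates from the survey for which the plan allows 10% missing data. For RQ5, deletion on missing moderators follows directly from the rule.

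**Conclusion.** The H5 sample size is correct for what it covers: 500 enrolled at 30% attrition gives 350 and 79.9% power at d=0.30, equal to the stated 80% within rounding. What is missing is a separate allowance for list-wise deletion among returned surveys, and the covariate rules give such deletion a route. If 2% to 10% of returned surveys were unusable, N would be about 343 to 315 and power about 79% to 76%. That range is assumed, its upper end is only an illustration borrowed from another survey, and the 30% may already include part of it. It therefore does not show that the study is underpowered. It shows an avoidable loss that a better analysis of the same data would largely prevent where the blank is in a covariate.

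**What to change.** For H5, replace the list-wise-deletion t-test on the change score with an analysis of 90-day minutes per week by imagery condition, adjusted for baseline minutes and sex, using full-information likelihood or multiple imputation. Covariates with missing values must be part of the likelihood or the imputation model. A standard regression or mixed model would still drop those cases. Full-information likelihood is already planned for the structural equation models, so the method is familiar to the study. RQ5 can use the same approach.

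In the H5 sample size paragraph, say whether the 30% includes returned surveys with unusable activity items. Do not enter 315 to 332 as the plan's own analysable number, because no rate in the documents supports it for H5.

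The cost is revised SAP wording and a little more analysis work, with no extra participants and no new data. The limits are that the method recovers little when the 90-day minutes themselves are missing, and that the gain from baseline adjustment depends on the baseline to 90-day correlation and the two SDs.
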